Participants who request to withdraw from the study or are lost to follow up will be referred back to the routine clinical service by the study team. Participants who develop a positive blood transcriptional biomarker at any point during longitudinal follow-up will then enter the LTBI treatment sub-study. Participants who develop a positive blood transcriptional biomarker or reach a study end point (Appendix 6) as a surrogate for progressive TB before 2 years, will be identified as progressors. Participants who complete 2 years follow up will be identified as non-progressors. Progressors and non-progressors will undergo routine clinical assessments to evaluate the need for any TB treatment when their participation in the study ends.

6. Recruitment and consent

Potential participants who meet the eligibility criteria will be identified by the routine tuberculosis clinical service and introduced to the study team. The study team will describe the study to these individuals, provide them with the participant information sheet, and answer their questions, in person, by telephone, by post or by email according to the participant's preferences. After at least 24 hours to consider this information, the study team will invite those who agree to participate to provide written informed consent.

For non-English speakers the study team will communicate with telephone translation services and provide translations of the participant information sheet and consent form. The original signed consent form will be filed in the study master file and a copy will be provided to the participant. All participants who are referred to the study team will be entered into a screening log with a record of their eligibility criteria, their decision to participate or reasons for declining to participate as appropriate.

7. Eligibility criteria

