9.1. Sample size and statistical power

We will recruit 400 LTBI contacts of active pulmonary TB cases to address the primary objective. This sample size is derived from estimated progression from LTBI to active TB within 2 years of 5%, giving 20 progressors and 380 non-progressors. Progressive disease may be due to a range of different immune responses, and each variation may only be evident in a subset of cases. Therefore, conventional differential gene expression analysis in the TST between groups of progressors and non-progressors, may not identify statistically significant differences. Instead, we will undertake supervised outlier profile analysis to identify gene expression among subsets of progressors, which lies outside the normal range measured in non-progressors. These methods provide robust statistical confidence by incorporating multiple testing corrections³²⁻³⁶, and have been successfully applied to discovery of novel oncogenic pathways^{32,37}. Using preliminary TST transcriptomic data from HIV negative individuals in computational simulations, we estimate >0.8 statistical power in this sample size to detect significant outlier traits among progressors (false discovery rate <0.05) when the outlier trait is shared by 5 or more progressors (Figure 2A). In order to identify eQTLs of TST transcriptomic data, we estimate that a sample size of 1000 is required to give >90% power to detect statistically significant correlations ($p < 10^{-8}$) for allelic frequencies $\geq 5\%$ depending on the correlation coefficients, as a composite measure of effect size and variance⁶¹. Finally, from our pilot data, we estimate that 15% of these individuals will express the blood transcriptional biomarker at time of recruitment to the study. Of these estimated 150 participants, 80 will be recruited to the LTBI treatment sub-study. Conservatively assuming that only 25% of patients decline LTBI therapy, a sample size of 68 participants will provide 80% power to detect a difference of 0.8 standard deviations (SDs) in signature scores between those who accept and decline treatment at each time point. This calculation assumes similar standard deviations among individuals in both groups. We have estimated 0.8SDs as the minimum difference in signature scores that is likely to be of clinical significance (based on the difference in mean scores between IGRA-positive and IGRA-negative TB case-contacts in our pilot data. To allow for losses to follow-up, 80 participants will be recruited.

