Appendix 5: Participant symptom questionnaire

1. Have you had a persistent cough for more than two weeks?
2. Have you lost weight in the last 3 months?
3. Have you experienced any drenching night sweats during the last 3 months?

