Appendix 6: Study end points

Participation in the study will end with any one of the following events and participants will go on to have routine clinical assessments to evaluate the need for LTBI or active TB treatment.

1. 2 year follow up completed
2. Changes in chest radiography (airspace shadowing or lymphadenopathy) consistent with progressive/active TB with at least one yes answer in the symptom questionnaire.
3. Two yes answers in the symptom questionnaire.

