Appendix 9: Risks to participants

Severity score- Low=can cause discomfort but unlikely to have an impact on health, Moderate=potential impact on health but unlikely to be life-threatening, Severe=definite impact on health and significant potential to be life-threatening.

Description of risk	Estimated incident rate	Severity	Justification
Progressive active TB as a result of deferring LTBI treatment in the longitudinal study.	<1%	Moderate	The two year cumulative risk of progressive TB in individuals being recruited to this study (IGRA positive contacts of active pulmonary TB) is estimated to be 5%. In routine clinical practice LTBI treatment is commonly offered to all such individuals. On the basis that this treatment is in fact not necessary for the vast majority, clinical review at 3-6 monthly intervals is widely used as an alternative approach. In the present study, we will undertake enhanced follow up at 3 monthly intervals with the addition of novel blood biomarkers with the potential to identify subclinical active TB representing an end point in their participation, when individuals will be offered treatment in line with standard clinical care. The available data on the predictive value of these biomarkers indicates that this approach minimises the 2 year cumulative risk of the development of symptomatic TB disease <1%. On the basis subclinical active TB will not meet conventional criteria for the diagnosis of symptomatic TB disease requiring full TB treatment, we expect that most participants who develop biomarkers of subclinical TB will be offered LTBI treatment. On the basis of being IGRA positive, all participants who complete 2 year follow up will be considered for LTBI treatment as per routine clinical practice. The risk of active TB is substantially lower after 2 years follow up, therefore these participants may opt not to accept LTBI treatment.

Description of risk	Estimated incident rate	Severity	Justification
Increased radiation exposure due to repeated chest radiographs	100%	Low	Participants may have up to 8 extra chest radiographs. Each of these is equivalent to 10 days of natural background radiation exposure, associated with a negligible additional cancer risk of <0.01%. This risk is substantially outweighed by the benefits of chest radiographic monitoring for evidence of progressive TB.
Discomfort during phlebotomy	10%	Low	The overall risk of harm is very low.

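### Two yes answers on the symptom questionnaire make a participant a progressor with no confirmation of TB, while the case group is sized on progression to active TB

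*Protocol*

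**What the plan says.** - **The label.** Section 5 of the protocol (Study schedule) has two routes to being a progressor. One is a positive blood transcriptional biomarker. The other covers those who "reach a study end point (Appendix 6) as a surrogate for progressive TB before 2 years, will be identified as progressors". Anyone followed for the full 2 years is a non-progressor.
- **The end points.** Appendix 6 lists three: completing 2 years; a chest radiograph change together with at least one symptom; and "Two yes answers in the symptom questionnaire".
- **The questionnaire.** Appendix 5 has three items: cough lasting over two weeks, weight loss, and drenching night sweats. The weight item reads "Have you lost weight in the last 3 months" and sets no amount and no condition on cause.
- **After exit.** Section 5 and Appendix 6 send participants to routine clinical assessment to decide on treatment. Section 8 refers anyone with evidence of active TB for urgent review. Neither result is said to feed back into the label.
- **The sample size.** Section 9.1: "This sample size is derived from estimated progression from LTBI to active TB within 2 years of 5%, giving 20 progressors and 380 non-progressors".
- **Surveillance linkage.** Section 9.2 finds progressors through national TB records among cross-sectional participants and among longitudinal participants who withdraw or are lost.
- **The biomarker as an end point.** Appendix 9 describes "novel blood biomarkers with the potential to identify subclinical active TB representing an end point in their participation". Appendix 6 does not list it.

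**The concern.** The primary objective compares skin-test responses of progressors and non-progressors, so the case definition carries the whole analysis. The event used for planning is active TB. The event that the label captures also includes two non-specific symptoms reported at one visit. Most of those answering the questionnaire every three months will not have TB, so even a low rate of unrelated symptoms can contribute materially to a case group planned at 20.

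The information that could settle each case is largely collected already. Blood and a radiograph are taken at every follow-up visit, and a clinical assessment follows exit. The case record form in Appendix 11 records only whether the participant continues, enters the treatment study or ends the study. It has no field for what the assessment found.

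In the other direction, a diagnosis of active TB is not itself an Appendix 6 event.

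**Working it through.** **1. The plan's own figure.** Section 9.1 gives 400 participants and 5% progression to active TB in 2 years. 400 × 0.05 = 20 and 400 × 0.95 = 380. The stated split reproduces exactly, as a count of active TB.

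**2. Visits at risk.** Follow-up is three-monthly for 2 years, so there are 8 visits. The progressor rule applies before 2 years, and month 24 is the completion end point. Visits at months 3 to 21 count: 7.

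**3. Assumption.** Let q be the chance that a participant without TB gives two or more yes answers at one visit. The protocol gives no value. I take 0.1% to 1%, independent across visits, with all 380 followed throughout and all 20 true cases captured.

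**4. Formulae.** False progressors F = 380 × (1 − (1 − q)^7). False share of the labelled group = F / (20 + F).

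| q per visit | F | False share |
|---|---|---|
| 0.1% | 2.7 | 2.7/22.7 = 12% |
| 0.25% | 6.6 | 6.6/26.6 = 25% |
| 0.5% | 13.1 | 13.1/33.1 = 40% |
| 1% | 25.8 | 25.8/45.8 = 56% |

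False labels equal the 20 true ones at 1 − (1 − 20/380)^(1/7) = 0.77% per visit. Counting the month-24 visit as well would give 3.0 false labels at 0.1% and 29.4 at 1%.

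**5. The other direction, by reading the rules together.** A participant with diagnosed TB becomes a progressor through a positive biomarker, two symptoms, or a radiograph change with a symptom. One who withdraws or is lost can be found by linkage. What remains is TB diagnosed in a participant who is biomarker-negative, has no qualifying symptom or radiograph event, and completes 2 years. Section 5 makes that person a non-progressor. The documents give no basis for a frequency, so I put no number on it.

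**6. Biomarker positivity.** Section 5 names it separately from Appendix 6 and moves such participants into the treatment sub-study. Appendix 9 calls it an end point of participation. Appendix 11 lists entering the treatment study and ending the study as different outcomes.

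**The case against.** The strongest reply is that the choice is disclosed: Section 5 calls these end points a surrogate, and handling of unconfirmed exits could sit in an analysis plan that is not shown. The disclosure is real. But the protocol itself fixes the classification rule, and calling it a surrogate does not explain why a later assessment that finds no TB should leave the label in place.

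The second reply is that the size rests on an assumed symptom rate. That stands. At the low end the contamination is about 3 people, and a reader who expects a lower rate will see less. The labelled group is also not simply 20 true cases plus false ones, because biomarker converters are progressors too. The table shows scale and is not a forecast.

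Two stronger readings are tempting and are not supported:

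- **That the stated power fails.** Section 9.1 bases its power of more than 0.8 on simulations that are not reproduced, at a false discovery rate below 0.05, "when the outlier trait is shared by 5 or more progressors". That condition is a count of sharers, not a proportion of the case group. Any tail probability computed from outside depends on where the edge of the normal range is set and on the multiplicity threshold, and plausible choices give opposite answers. The stated power cannot be checked and is not disputed here.
- **That diagnosed TB is left out of the classification.** The biomarker route in Section 5 and the linkage in Section 9.2 cover much of it. Only the narrow gap in step 5 remains.

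The mismatch between Appendix 6 and Appendix 9 is likewise limited. Section 5 makes biomarker-positive participants progressors on either reading, so the passages need reconciling but the label does not turn on them.

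**Conclusion.** The point holds for the research label. As written, two yes answers before 2 years make a participant a progressor, and no later evidence can reverse it, although the case group was sized on active TB. Under an assumed 0.1% to 1% per visit, independent visits and full capture of the 20 true cases, the seven qualifying visits add about 3 to 26 false progressors, about 12% to 56% of those labelled. The defect in the rule does not depend on that range; only its size does. Misclassification the other way is possible but narrow and unquantified. Nothing here bears on when participants should leave follow-up or be treated.

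**What to change.** Leave the exit rule and clinical care unchanged, and change only the analysis label:

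1. In the primary comparison, count a participant who exits on symptoms or radiograph as a progressor only if the subsequent routine assessment or surveillance linkage records active TB, or the blood biomarker is positive.
2. Exclude other such exits from the primary comparison as unclassified, and report how many there are. Keep the label as written for a sensitivity analysis.
3. Count active TB diagnosed or notified within 2 years as progression for every longitudinal participant, and extend the surveillance linkage to all of them.
4. Add a field to the Appendix 11 case record form for the result of the clinical assessment.
5. Reconcile Section 5, Appendix 6 and Appendix 9 on whether biomarker positivity is an end point.

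The cost is about one paragraph of protocol text, one form field and a wider use of a linkage already planned for other participants. The downside is fewer nominal progressors in a case group that is already small.

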Appendix 8: Immunomodulatory drugs

Systemic corticosteroids

Azothioprine

Corticosteroids

Cyclosporin,

FK506

Methotrexate

Tacrolimus

Anti-TNF (adalimumab, etanercept)

Appendix 9: Risks to participants

Severity score- Low=can cause discomfort but unlikely to have an impact on health, Moderate=potential impact on health but unlikely to be life-threatening, Severe=definite impact on health and significant potential to be life-threatening.

Description of risk	Estimated incident rate	Severity	Justification
Progressive active TB as a result of deferring LTBI treatment in the longitudinal study.	<1%	Moderate	The two year cumulative risk of progressive TB in individuals being recruited to this study (IGRA positive contacts of active pulmonary TB) is estimated to be 5%. In routine clinical practice LTBI treatment is commonly offered to all such individuals. On the basis that this treatment is in fact not necessary for the vast majority, clinical review at 3-6 monthly intervals is widely used as an alternative approach. In the present study, we will undertake enhanced follow up at 3 monthly intervals with the addition of novel blood biomarkers with the potential to identify subclinical active TB representing an end point in their participation, when individuals will be offered treatment in line with standard clinical care. The available data on the predictive value of these biomarkers indicates that this approach minimises the 2 year cumulative risk of the development of symptomatic TB disease <1%. On the basis subclinical active TB will not meet conventional criteria for the diagnosis of symptomatic TB disease requiring full TB treatment, we expect that most participants who develop biomarkers of subclinical TB will be offered LTBI treatment. On the basis of being IGRA positive, all participants who complete 2 year follow up will be considered for LTBI treatment as per routine clinical practice. The risk of active TB is substantially lower after 2 years follow up, therefore these participants may opt not to accept LTBI treatment.

Description of risk	Estimated incident rate	Severity	Justification
Increased radiation exposure due to repeated chest radiographs	100%	Low	Participants may have up to 8 extra chest radiographs. Each of these is equivalent to 10 days of natural background radiation exposure, associated with a negligible additional cancer risk of <0.01%. This risk is substantially outweighed by the benefits of chest radiographic monitoring for evidence of progressive TB.
Discomfort during phlebotomy	10%	Low	The overall risk of harm is very low.
Brief discomfort during local anaesthetic injection	10%	Low	The overall risk of harm is very low.
Allergic reaction to local anaesthetic (People with a history of allergic reaction to local anaesthetics will be excluded)	<1%	Moderate	People with a history of allergic reaction to local anaesthetics will be excluded. The overall risk of harm is very low.
Pain at the biopsy site	5%	Low	The overall risk of harm is very low.
Bleeding at the biopsy site	<5%	Low	The overall risk of harm is very low.
Infection of the biopsy site	<1%	Moderate	The overall risk of harm is very low.
Minor residual (after 3-6 months) scarring of the biopsy site	10%	Low	People with a history of keloid scarring will be excluded. The overall risk of harm is very low.

Appendix 10: Adverse events

Definitions

Term	Definition
“Adverse Event (AE)”	Means any untoward medical occurrence in a subject to whom a medicinal product has been administered, including occurrences which are not necessarily caused by or related to that product.
“Adverse Reaction (AR)”	Means any untoward and unintended response in a subject to an investigational medicinal product which is related to any dose administered to that subject.
“Serious Adverse Event (SAE), “Serious Adverse Reaction, or Unexpected Serious Adverse Reaction”	means an adverse event, adverse reaction or unexpected adverse reaction respectively that 
 - results in death - is life threatening - requires hospitalisation or prolongation of existing hospitalisation - results in persistent or significant disability or incapacity or - consists of a congenital anomaly or birth defect
“Suspected Serious Adverse Reaction (SSAR)”	means an adverse reaction that is classed in nature as serious and which is consistent with the information about the medicinal product in question set out
	in the case of a licensed product, in the summary of product characteristics (SmPC) for that product
	(b) in the case of any other investigational medicinal product, in the Investigator’s Brochure (IB) relating to the trial in question
“Suspected Unexpected Serious Adverse Reaction (SUSAR)”	means an adverse reaction that is classed in nature as serious and which is not consistent with the information about the medicinal product in question set out
	in the case of a licensed product, in the summary of product characteristics (SmPC) for that product
	in the case of any other investigational medicinal product, in the IB relating to the trial in question

Adverse event reporting form

Study sponsor ID number	
Subject initials	
Subject (study) UIN	

Description of Adverse Event		
Date of onset		
Outcome	Resolved without residual effect	
	Resolved with residual effect	
	Continuing	
	Death	
Date of Resolution		
Severity Grade	Mild	
	Moderate	
	Severe	
Casualty Assessment	Not related	
	Possibly related	
	Probably related	
	Definitely related	
Is it Serious	Results in death	
	Is life threatening	
	Requires hospitalisation or prolongation of existing hospitalisation	
	Results in persistent or significant disability or incapacity	
	Consists of congenital anomaly or birth defect	
	No	

These qualify an Adverse event (AE) as an Adverse Reaction (AR)

Please complete SAE reporting form and email to UCL Biomedicine R&D Unit within 24hrs: [contact]

Serious Adverse Event Reporting Form

Definition of SAE:
An SAE can be defined as: an untoward medical occurrence in a subject during clinical research involving a pharmaceutical product, medical device, or clinical intervention that: is fatal; is life threatening; results in persistent or significant disability / incapacity; requires inpatient hospitalisation or prolongs a current hospitalisation; results in a congenital anomaly in offspring; or an event that may jeopardise the patient or may require intervention to prevent one of the outcomes listed above.
Initial Reporting:
For all initial reporting of any Serious Adverse Events / Incidents this form must be completed fully and sent to the UCL Joint Research Office ([contact]) within 24 hours of the incident occurring or being known.
Follow-up Information:
For subsequent follow-up reporting of an SAE, a new SAE reporting form should be completed with just administration details and sections A, D, E and G only and forwarded to the UCL Biomedicine R&D Unit as soon as possible. All SAEs must be followed up until closure.
SUSARs/Expedited Reporting:
For any Suspected Unexpected Serious Adverse Reactions (SUSARs) which are life threatening/fatal, initial reports must be sent to the Competent Authority and the Main Ethics Committee by the sponsor within 7 days of being aware of the event. Follow-up information must be sent to the Competent Authority and Main Ethics Committee within 8 days after initial reporting. All other SUSARs must be reported within 15 days and any follow up information sent to the Competent Authority and Main Ethics Committee as soon as possible. A copy of these reports must be sent to the UCL Biomedicine R&D Unit if this duty has been delegated by the sponsor to the CI.

Initial report		Follow up report		Reporting date	
Study Title					
Ethics Ref No					
R&D Ref No					

Section A – Details of subject affected by Serious Adverse Event					
Has the chief Investigator been informed of this event prior to completion of this form?					
Subject initials		Subject DOB		Subject UIN	
Gender		Height		Weight	

Section B – Details of the Serious Adverse Event			
Date of event onset		Time of event onset	
Site		Exact location	
Study intervention			
Time of intervention			
Type of serious adverse event			
Subject died			

Life threatening	
In-patient hospitalisation or prolongation	
Persistent or significant disability/incapacity	
Congenital anomaly/ birth defect	
Medically important event	
Other	

Describe Event: Give a summary of signs and symptoms including vital signs, diagnosis, treatment of event, concurrent treatment and other relevant medical history. Please include the point in the study at which the event occurred.

Section C – Relationship To Study Involvement				
Was the incident related to the subject’s involvement in the study?	Yes		No	
Is the event related to the study intervention?	Yes		No	
Was this expected by the Chief Investigator?	Yes		No	
Was this expected by the Sponsor?	Yes		No	
Is the event related to the study intervention?	Yes		No	
Give details if sponsor’s and CI/PI evaluation of expectedness differ				
Severity grading	Mild		Moderate	
			Severe	
Action taken regarding subject’s participation in the study				
Temporarily discontinued		Permanently discontinued		Subject continued
				
Date		Decision taken by		
Explain the reasons for the decision				

Section D – Outcome of Serious Adverse Event	
Recovered	
Not yet recovered	
Alive with sequelae	
Subject died	
Give details	

Section E – Details of Reporter and Site Chief Investigator	
Name of person completing this report	
Role	
Affiliation	
Contact details (email)	
Reporter signature	Date

Chief investigator signature	Date
------------------------------	------

Section F – Circulation				
Date form completed				
Date CI informed				
Date Ethics Committee informed				
Did this event require an expedited report?	Yes		No	
If yes please provide date reported to the Competent Authority (ies)/Main Ethics Committee				
Please list name(s) of the Competent Authority(ies)/Main Ethics Committee reports sent to				

Section G – Follow-up Information	
Date completed	
Additional information to describe progress of event	

Please forward a copy of this form to the UCL Joint Research Office ([contact]).
The original form should be kept in the Study/Trial Master File.

UCL Joint Research Office use only			
R&D Reference No			
Date received		Date reviewed	
Did this event require further action	Yes	No	
If yes, provide details of action taken:			
Reviewed by			
Signed		Date	

